# 7.6.2.3 Other Secondary Efficacy Endpoints

Descriptive statistics for the other secondary efficacy endpoints will be presented by treatment group and by study visit where appropriate.

For time-to-event endpoints, similar methods will be used as specified for the analyses of the primary variable. For binary endpoints, the treatment group comparisons will be performed at Day 8 only, with descriptive statistics provided for each clinic visit.

• Percentage of patients in each study group who require hospital re-admission related to COVID-19 through Day 31.

The percentage of patients who require re-admission for COVID-19 related signs or symptoms through Day 31 will be presented by treatment group and Clopper–Pearson 95% CI will be computed for the binomial proportion.

Only patients who discharged from the hospital will be included in the analysis of the re-admission for COVID-19 related signs or symptoms.

• Percentage of patients in each study group and in each of the categories of the 11-point WHO Clinical Progression Scale on Days 4, 8, 15, and 31.

The clinical status, as assessed on the 11-point WHO Clinical Progression Scale will be summarised on Days 4, 8, 15, and 31, by treatment group.

In case of missing clinical status at the time point, the following approach will be used:

- If patient dies before or on the time point → clinical status = 10.
- Otherwise, LOCF approach will be used, where the last recorded clinical status for the same patient is carried forward to the missing clinical status at the time point.
- Percentage of patients in each study group requiring oxygen therapy on Days 4, 8, 15, and 31.

The percentage of patients who require oxygen therapy on Days 4, 8, 15, and 31, will be presented by treatment group. Clopper–Pearson 95% CI will be computed for the binomial proportions.

If a patient requires any change in the oxygen therapy on Day 4, 8, 15, or 31, the new oxygen status will be selected, e.g. if a patient changes from "Low-flow" to "No supplemental oxygen needed" on Day 4, "Require oxygen therapy on Day 4'' = No. On the other hand, if a patient changes from "No supplemental oxygen needed" to "Low-flow" on Day 8, "Require oxygen therapy on Day 8" = Yes.

The difference in the percentage of patients who require oxygen therapy on Days 4, 8, 15, and 31 between each dose of plitidepsin versus control arm

will be presented for each dose of plitidepsin and the exact 95% CI will be computed for the difference in the percentage.

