
The oxygen therapy rate on Day 8 between each dose of plitidepsin versus control arm will be compared using a stratified logistic regression model. The model will be adjusted for the randomisation stratification factors. The odds ratios, 95% CIs, and 2-sided p-values for the comparison of each dose of plitidepsin versus control arm will be presented.

Moreover, the percentage of patients who require oxygen therapy at some time from Day 1 to Day 4, from Day 1 to Day 8, from Day 1 to Day 15, and from Day 1 to Day 31, will be presented by treatment group. Clopper– Pearson 95% CI will be computed for the binomial proportions.

The difference in the percentage of patients who require oxygen therapy at some time during each period between each dose of plitidepsin versus control arm will be presented for each dose of plitidepsin and the exact 95% CI will be computed for the difference in the percentage.

The percentage of patients who require oxygen therapy at some time from Day 1 to Day 8 between each dose of plitidepsin versus control arm will be compared using a stratified logistic regression model. The model will be adjusted for the randomisation stratification factors. The odds ratios, 95% CIs, and 2-sided p-values for the comparison of each dose of plitidepsin versus control arm will be presented.

• *Time to intensification of respiratory support (WHO >6 [intubation]).* 

Time to intensification of respiratory support (in days), defined as the first day, from randomisation through completion of the study, on which a patient satisfies a category > 6 on the 11-point WHO Clinical Progression Scale.

Patients who reported a category > 6 on the 11-point WHO Clinical Progression Scale or died due to any cause through the study will be considered as an event on the first day on which a patient satisfies a category > 6 on the 11-point WHO Clinical Progression Scale or date of death, whichever occurs first. Otherwise, patients will be censored at the date of the last visit or telephone contact with the patient.

Time-to intensification of respiratory support (days) = (date of event or censoring – date of randomisation)

If date of event is the same as the randomisation date then time-to intensification of respiratory support will be considered as 1 day. If no data is available then time will be censored at time 0.

CONFIDENTIAL

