Time-to intensification of respiratory support will be analysed using the Kaplan-Meier method and 25th percentile, median and 75th percentile time will be presented by treatment group together with 95% CIs. The 95% CIs will be computed based on Brookmeyer-Crowley method and using a log log transformation. The mean time to intensification of respiratory support and its standard error will be also presented by treatment group.

Time-to intensification of respiratory support between each dose of plitidepsin versus control arm will be compared using a stratified log-rank test, including the randomisation stratification factors as covariates, ie, Geographical Region (Europe vs. Rest of the World), Charlson Comorbidity index (0-1 vs. >1) and pre-baseline Barthel index ( $\geq$ 90 versus <90) as derived using the eCRF data. The 2-sided p-values for the comparison of each dose of plitidepsin versus control arm will be presented.

A stratified Cox proportional-hazards regression model, including the randomisation stratification factors as covariates, will be applied to compare results between each dose of plitidepsin versus control arm. Hazard ratios, 95% CIs, and 2-sided p-values for the comparison of each dose of plitidepsin versus control arm will be presented. The cumulative survival will be displayed graphically by treatment group using a Kaplan-Meier curve.

• Total duration of ICU stay for each study group.

The total duration of ICU stay (in days), defined as the number of days in ICU

Duration of ICU stay (days) = (last date in ICU – date of admission in ICU) + 1 – off-ICU days

The number and percentage of patients who were admitted in ICU together with the total duration of ICU stay (in days) will be summarised by treatment group.

Only patients who were admitted in ICU will be included in the analysis of the duration of ICU stay.

• Percentage of patients in each study group requiring high-flow oxygen on Days 4, 8, 15, and 31.

The percentage of patients who require high-flow oxygen on Days 4, 8, 15, and 31, will be presented by treatment group. Clopper–Pearson 95% CI will be computed for the binomial proportions.

Similarly, this endpoint will be analyzed as oxygen therapy rate.

• Percentage of patients in each study group requiring non-invasive mechanical ventilation on Days 4, 8, 15, and 31.

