The percentage of patients who require non-invasive mechanical ventilation on Days 4, 8, 15, and 31, will be presented by treatment group. Clopper– Pearson 95% CI will be computed for the binomial proportions.

Similarly, this endpoint will be analyzed as oxygen therapy rate.

• Percentage of patients in each study group requiring invasive mechanical ventilation or ECMO on Days 4, 8, 15, and 31.

The percentage of patients who require invasive mechanical ventilation or ECMO on Days 4, 8, 15, and 31, will be presented by treatment group. Clopper–Pearson 95% CI will be computed for the binomial proportions.

Similarly, this endpoint will be analyzed as oxygen therapy rate.

• Time to initiation with immune-modulating drugs.

Time to initiation with immune-modulating drugs, defined as the first day, from randomisation through completion of the study, on which a patient receives subsequent immune-modulating drugs.

Patients who started subsequent immune-modulating drugs will be considered as an event on the first date of starting a subsequent immunemodulating drug. Otherwise, in case of early study discontinuation due to any reason the patient will be censored at the date of the early study discontinuation. Otherwise, the patient will be censored at the date of the Day 31 visit or death date, whichever is first.

Time-to initiation with immune-modulating drugs (days) = (date of event or censoring – date of randomisation)

If date of event is the same as the randomisation date then time-to initiation with immune-modulating drugs will be considered as 1 day. If no data is available then time will be censored at time 0.

Time-to initiation with immune-modulating drugs will be analysed using the Kaplan-Meier method and 25th percentile, median and 75th percentile time will be presented by treatment group together with 95% CIs. The 95% CIs will be computed based on Brookmeyer-Crowley method and using a log log transformation. The mean time to initiation with immune-modulating drugs and its standard error will be also presented by treatment group.

Time-to initiation with immune-modulating drugs between each dose of plitidepsin versus control arm will be compared using a stratified log-rank test, including the randomisation stratification factors as covariates, ie, Geographical Region (Europe vs. Rest of the World), and Charlson Comorbidity index (0-1 vs. >1) and pre-baseline Barthel index ( $\geq$ 90 versus

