## Table 14.2.3.9.1 Patients who Require High-Flow Oxygen (Full Analysis Set)

Timepoint Variable	Plitidepsin 2.5mg (N=XXX)	Plitidepsin 1.5mg (N=XXX)	Control Arm (N=XXX)
Day 4			
Patients at Day 4, n1	XXX	XXX	XXX
Require High-Flow Oxygen, n (%)	xx (xx.x)	xx (xx.x)	xx (xx.x)
95% CI for Require High-Flow Oxygen (%) [a]	XX.X - XX.X	XX.X - XX.X	XX.X - XX.X
Non Require High-Flow Oxygen, n (%)	xx (xx.x)	xx (xx.x)	xx (xx.x)
Difference of High-Flow Oxygen Rate (%) [b]	XX.X	XX.X	
95% CI for Difference of High-Flow Oxygen Rate (%) [c]	XX.X – XX.X	XX.X - XX.X	
Day 8			
Patients at Day 8, n1	XXX	XXX	XXX
Require High-Flow Oxygen, n (%)	xx (xx.x)	xx (xx.x)	xx (xx.x)
95% CI for Require High-Flow Oxygen (%) [a]	xx.x - xx.x	xx.x - xx.x	xx.x - xx.x
Non Require High-Flow Oxygen, n (%)	xx (xx.x)	xx (xx.x)	xx (xx.x)
Difference of High-Flow Oxygen Rate (%) [b]	xx.x	XX.X	
95% CI for Difference of High-Flow Oxygen Rate (%) [c]	XX.X - XX.X	XX.X - XX.X	
Adjusted Odds Ratio [d,e]	X.XXX	X.XXX	
95% CI for Adjusted Odds Ratio [d,e]	x.xxx - x.xxx	x.xxx - x.xxx	
2-sided p-value [d]	X.XXX	X.XXX	
Day 15			
Patients at Day 15, n1	XXX	XXX	XXX
Require High-Flow Oxygen, n (%)	xx (xx.x)	xx (xx.x)	xx (xx.x)
95% CI for Require High-Flow Oxygen (%) [a]	XX.X - XX.X	XX.X - XX.X	xx.x - xx.x
Non Require High-Flow Oxygen, n (%)	xx (xx.x)	xx (xx.x)	xx (xx.x)
Difference of High-Flow Oxygen Rate (%) [b]	XX.X	XX.X	
95% CI for Difference of High-Flow Oxygen Rate (%) [c]	XX.X - XX.X	XX.X - XX.X	

Day 31			
Patients at Day 31, n1	XXX	XXX	XXX
Require High-Flow Oxygen, n (%)	xx (xx.x)	xx (xx.x)	xx (xx.x)
95% CI for Require High-Flow Oxygen (%) [a]	XX.X - XX.X	XX.X - XX.X	XX.X - XX.X
Non Require High-Flow Oxygen, n (%)	xx (xx.x)	xx (xx.x)	xx (xx.x)
Difference of High-Flow Oxygen Rate (%) [b]	XX.X	XX.X	
95% CI for Difference of High-Flow Oxygen Rate (%) [c]	XX.X – XX.X	XX.X - XX.X	

N = number of patients in analysis set; n = number of patients in each category; n1 = number of patients with data available at timepoint; % = percentages are calculated based on n1 as the denominator; CI = Confidence interval.

[a] Clopper-Pearson 95% confidence interval.

[b] Difference of High-Flow Oxygen Rate = High-Flow Oxygen Rate for the plitidepsin arm - High-Flow Oxygen Rate for control arm.

[c] Exact 95% confidence interval.

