[d] Adjusted Odds Ratio, 95% CI and 2-sided p-values based on a stratified logistic regression model with fixed effects of treatment group and randomisation stratification factors, ie, geographical region (Europe vs. Rest of the World), Charlson Comorbidity Index (0-1 vs. >1) and pre-baseline Barthel index (≥90 versus <90) as derived using the eCRF data as covariates. [e] Statistics calculated relative to Control Arm.

Reference: Listing 16.2.6.4

Programming notes (not part of the table):

Table 14.2.3.10.1 Patients who Rec	uire Non-invasive Mechanical	Ventilation (Full Analysis Set)
	an e rion mitabrie fileenamear	(I un That sis set)

Timepoint Variable	Plitidepsin 2.5mg (N=XXX)	Plitidepsin 1.5mg (N=XXX)	Control Arm (N=XXX)
Day 4			
Patients at Day 4, n1	XXX	XXX	XXX
Require Non-invasive Mechanical Ventilation, n (%)	xx (xx.x)	xx (xx.x)	xx (xx.x)
95% CI for Require Non-invasive Mechanical Ventilation (%) [a]	$\mathbf{x}\mathbf{x}.\mathbf{x} - \mathbf{x}\mathbf{x}.\mathbf{x}$	XX.X - XX.X	XX.X - XX.X
Non Require Non-invasive Mechanical Ventilation, n (%)	xx (xx.x)	xx (xx.x)	xx (xx.x)
Difference of Non-invasive Mechanical Ventilation Rate (%) [b]	XX.X	XX.X	
95% CI for Difference of Non-invasive Mechanical Ventilation Rate (%) [c]	XX.X - XX.X	XX.X - XX.X	
Day 8			
Patients at Day 8, n1	XXX	XXX	XXX
Require Non-invasive Mechanical Ventilation, n (%)	xx (xx.x)	xx (xx.x)	xx (xx.x)
95% CI for Require Non-invasive Mechanical Ventilation (%) [a]	XX.X - XX.X	XX.X - XX.X	XX.X - XX.X
Non Require Non-invasive Mechanical Ventilation, n (%)	xx (xx.x)	xx (xx.x)	xx (xx.x)
Difference of Non-invasive Mechanical Ventilation Rate (%) [b]	XX.X	XX.X	
95% CI for Difference of Non-invasive Mechanical Ventilation Rate (%) [c]	XX.X - XX.X	XX.X - XX.X	
Adjusted Odds Ratio [d,e]	X.XXX	X.XXX	
95% CI for Adjusted Odds Ratio [d,e]	x.xxx - x.xxx	x.xxx - x.xxx	
2-sided p-value [d]	X.XXX	X.XXX	
Day 15			
Patients at Day 15, n1	XXX	XXX	XXX
Require Non-invasive Mechanical Ventilation, n (%)	xx (xx.x)	xx (xx.x)	xx (xx.x)
95% CI for Require Non-invasive Mechanical Ventilation (%) [a]	XX.X - XX.X	XX.X - XX.X	XX.X - XX.X
Non Require Non-invasive Mechanical Ventilation, n (%)	xx (xx.x)	xx (xx.x)	xx (xx.x)
Difference of Non-invasive Mechanical Ventilation Rate (%) [b]	XX.X	XX.X	
95% CI for Difference of Non-invasive Mechanical Ventilation Rate (%) [c]	XX.X - XX.X	XX.X - XX.X	

Day 31			
Patients at Day 31, n1	XXX	XXX	XXX

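### The Day 8 high-flow and NIV rates count one device only, so an odds ratio below 1 can reflect deterioration rather than benefit

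*SAP*

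**What the plan says.** SAP Section 7.6.2.3 sets the by-day high-flow rate ("The percentage of patients who require high-flow oxygen on Days 4, 8, 15, and 31, will be presented by treatment group") and words the NIV rate the same way ("The percentage of patients who require non-invasive mechanical ventilation on Days 4, 8, 15, and 31, will be presented by treatment group"). For each it adds "Similarly, this endpoint will be analyzed as oxygen therapy rate". That brings over three elements of the oxygen therapy rate:

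- **Status rule:** "If a patient requires any change in the oxygen therapy on Day 4, 8, 15, or 31, the new oxygen status will be selected".
- **Day 8 test:** "The oxygen therapy rate on Day 8 between each dose of plitidepsin versus control arm will be compared using a stratified logistic regression model", reported with odds ratio, 95% CI and two-sided p-value.
- **Per-period version:** "the percentage of patients who require oxygen therapy at some time from Day 1 to Day 4", and likewise to Days 8, 15 and 31, with the same test for Day 1 to Day 8.

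The table shells make each outcome binary. The complement rows read "Non Require High-Flow Oxygen, n" in Table 14.2.3.9.1 and "Non Require Non-invasive Mechanical Ventilation, n" in the NIV shells. The by-day tables divide by n1, the patients with data at that timepoint. The per-period tables divide by N. The source is Listing 16.2.6.4, whose shell shows one oxygen status per record. Invasive ventilation or ECMO has its own separate rate (Tables 14.2.3.11.1 and 14.2.3.11.2).

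Nothing says that a patient on a higher level of support counts as requiring the lower one, and no rule covers deaths in these rates. The SAP addendum repeats the tables for site ES40 and for all other sites.

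**The concern.** These rates belong with the objective of comparing the need for intensified respiratory or intensive care support (SAP Section 2.1.3.3), where less support is presumably better. With a device-only definition, the *Non Require* row mixes patients who have improved with patients who have moved past the device to a ventilator. A patient moved from high flow to NIV likewise leaves the high-flow count. An arm can thus lower its high-flow or NIV rate by getting worse. Because a Day 8 odds ratio and p-value are attached to each table, a low odds ratio invites a reading of benefit that the definition does not support.

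**Working it through.** The SAP gives no figure for these rates, so there is none to reproduce. The check first reads the scoring rule, then runs an assumed example to show direction and size.

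**Scoring of a Day 8 patient under the by-day rule**

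| Status on Day 8 | High-flow table | NIV table |
|---|---|---|
| No oxygen or low flow | Non Require | Non Require |
| High flow | Require | Non Require |
| NIV | Non Require | Require |
| Invasive ventilation or ECMO | Non Require | Non Require |
| Dead by Day 8 | expected outside n1 | expected outside n1 |

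The last two rows are inferred from the new-status rule, the single status per record in Listing 16.2.6.4 and the n1 denominator.

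**Example, planned size**

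Inputs: 203 per arm (SAP Section 2.2). Assumed, not in the SAP: 30 per arm need high flow or more on Day 8, no one is on NIV, and 20% of the 30 are intubated or on ECMO in control against 60% in plitidepsin. Formula: OR = [a/(n−a)] / [b/(n−b)], with a for plitidepsin and b for control. P-values are Wald. The planned model also adjusts for the stratification factors; this example does not.

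- High flow only: 12 v 24. OR = (12/191)/(24/179) = 0.47. The standard error of log OR is √(1/12+1/191+1/24+1/179) = 0.369, so z = −2.06 and p = 0.040.
- High flow or higher: 30 v 30. OR = 1.00.
- Invasive or ECMO: 18 v 6. OR = (18/185)/(6/197) = 3.20, p = 0.016.

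**Range:** with 20, 30 or 41 per arm needing support, control escalation at 20% and plitidepsin escalation from 20% to 80%, the device-only OR runs from 1.00 down to 0.21. The lowest value is (8/195)/(33/170). The *or higher* OR stays at 1.00 throughout.

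**Per-period tables, same 30-patient case:** the result depends on how many escalated patients used high flow first.

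- None did: 12 v 24, OR 0.47.
- Half did: 21 v 27, OR = (21/182)/(27/176) = 0.75.
- All did: 30 v 30, OR 1.00.

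A patient who went from NIV to intubation remains *Require* in the per-period NIV table.

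**Why a death rule is needed:** suppose 6 of the 18 escalated plitidepsin patients had died instead, and left n1.

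- High flow or higher without a death rule: 24/197 v 30/203, OR = (24/173)/(30/173) = 0.80.
- Deaths counted as requiring support: 30/203 v 30/203, OR = 1.00.

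A cumulative tier alone would still be biased.

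**Smaller trial:** SAP Section 8 says recruitment stopped before 33% of events. Assume 65 per arm on Day 8, with high flow, NIV and invasive counts of 5, 2, 7 (plitidepsin) and 10, 2, 2 (control).

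- High flow only: OR = (5/60)/(10/55) = 0.46, p about 0.18.
- High flow or higher: 14 v 14, OR = 1.0.
- NIV only: 2 v 2, OR = 1.0.
- NIV or higher: 9 v 4, OR = (9/56)/(4/61) = 2.45.

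At this size the trouble is the direction of the estimate, not a significant result.

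**The case against.** Several points on the other side are sound.

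- **The scoring is inferred.** The SAP does not say in words that an intubated patient is *Non Require*, and its examples of a changed status cover only low flow and no oxygen. The eCRF and dataset specifications are not shown. It remains the natural reading, and if something else is meant the SAP should say so.
- **The favourable direction is not stated.** The high-flow and NIV shells carry no footnote on which odds ratio favours plitidepsin, unlike the hazard-ratio shells. A reader might infer that the SAP declares an odds ratio below 1 to be benefit. It does not; the direction follows only from the objective.
- **The per-period tables are largely sound.** A reader might extend the point to every high-flow and NIV rate. The documents do not support that, because a patient who used the device at any time in the period stays *Require*.
- **Escalation is captured elsewhere.** The invasive/ECMO rate is tested in the same way. Time to WHO category above 6 counts death as an event. Day 8 WHO status has a proportional odds analysis. Table 14.2.3.2 gives the share of patients who ever needed any advanced support. In both examples above, the invasive/ECMO rate points the other way.
- **The WHO scale puts NIV and high flow in one category.** An *NIV or higher* tier therefore uses an ordering which that scale does not.

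These points narrow the concern to the by-day tables. They do not remove it: a p-value in Tables 14.2.3.9.1 and 14.2.3.10.1 that can move in the favourable direction through intubation or death is not made interpretable by other tables.

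**Conclusion.** The point holds for the by-day rates in Tables 14.2.3.9.1 and 14.2.3.10.1 and for their ES40 and non-ES40 repeats. On the natural reading, the Day 8 odds ratio can fall below 1 because patients moved to higher support or died. The per-period tables (14.2.3.9.2 and 14.2.3.10.2) share this only for patients who reach higher support, or die, without ever using the device in question.

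The size depends on how far escalation differs between arms, which the SAP does not give. With equal need for support, the assumed range is a device-only odds ratio of 1.00 (no difference in escalation) to 0.21.

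A reader might conclude that the trial's efficacy result is at risk. The documents do not support that. These are other secondary endpoints outside the Hochberg procedure, and the primary and key secondary analyses do not use them. What is affected is how these particular comparisons can be read.

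**What to change.** In SAP Section 7.6.2.3, Tables 14.2.3.9.1 and 14.2.3.10.1 and their addendum repeats:

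1. Apply the Day 8 odds ratio and p-value to high-flow oxygen or higher support (NIV, invasive ventilation, ECMO), and to NIV or higher support (invasive ventilation, ECMO).
2. Count a death on or before the timepoint as requiring support and keep the patient in the denominator. This matches the SAP's own rule that scores WHO status as 10 when a patient has died by the timepoint.
3. Keep the device-specific counts as descriptive rows, without odds ratio or p-value.
4. State which direction of the odds ratio favours plitidepsin.

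The same definition can be used for the Day 1 to Day 8 comparison in the per-period tables, where it changes less.

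The cost is a wording change and a recode of data already collected; Section 7.6.2.2 already pools these devices as advanced oxygen support. The tested rate no longer describes use of a single device, but the descriptive rows still do. The addendum dates database lock to 26 April 2023, so a change made after that should be labelled post hoc.

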The date at which the patient was last known to be alive will be the latest date obtained from: visit/assessment dates (with valid assessment measures, ie, non-blank), AE start and stop dates (except AEs with fatal outcome), concomitant medications start and stop dates and concomitant procedure dates.

**Note**: For the interim analysis, overall survival is defined as the elapsed time to death if a patient died on or prior to the cutoff date. If a patient's live/death status is known between cutoff date and the actual interim analysis extract date, then the patient is censored on the cutoff date. Otherwise, if a patient is only known to be alive prior to the cutoff date, then the patient is censored at the last known alive date.

Overall survival will be analysed using the Kaplan-Meier method and 25th percentile, median and 75th percentile time will be presented by treatment group together with 95% CIs. The 95% CIs will be computed based on Brookmeyer-Crowley method and using a log log transformation. The mean survival time and its standard error will be also presented by treatment group. Additionally, mortality rates by Days 4, 8, 15, and 31 will be presented together with 95% confidence bands. The 95% confidence bands will be computed based on Hall-Wellner method.

Overall survival between each dose of plitidepsin versus control arm will be compared using a stratified log-rank test, including the randomisation stratification factors as covariates, ie, Geographical Region (Europe vs. Rest of the World), Charlson Comorbidity index (0-1 vs. >1) and pre-baseline Barthel index (≥90 versus <90) as derived using the eCRF data. The 2-sided p-values for the comparison of each dose of plitidepsin versus control arm will be presented.

A stratified Cox proportional-hazards regression model, including the randomisation stratification factors as covariates, will be applied to compare results between each dose of plitidepsin versus control arm. Hazard ratios, 95% CIs, and 2-sided p-values for the comparison of each dose of plitidepsin versus control arm will be presented. The cumulative proportion of mortality (1-cumulative survival) will be displayed graphically by treatment group using a Kaplan-Meier curve.

• Change in the viral load of SARS-CoV-2 in each study group from Day 1 before administration of study drug until Day 8.

The change (log10 copies/mL) from Day 1 visit to Day 8 visit will be calculated as the difference between Day 1 and Day 8 values, ie,

change from Day 1 = Day 8 value - Day 1 value

The viral load of SARS-CoV-2 (log10 copies/mL) at Day 1 and Day 8, and the change from Day 1 in SARS-CoV-2 viral load at Day 8 will be summarized using standard descriptive statistics. Data from all study visits, scheduled and unscheduled, will be listed.

CONFIDENTIAL

The change in viral load of SARS-CoV-2 at Day 8 between each dose of plitidepsin versus control arm will be compared using an analysis of covariance (ANCOVA) model fitted for the fixed effects of treatment group, the randomisation stratification factors, and the continuous fixed covariate of viral load of SARS-CoV-2 at Day 1.

The least squares (LS) means and SE for each treatment group, together with the LS mean differences, SE, 95% CIs, and 2-sided p-values for the comparison of each dose of plitidepsin versus control arm will be presented.

Median viral load of SARS-CoV-2 together with the interquartile range will be plotted at Day 1 and Day 8.

**Note**: Prior to calculation of summary statistics: any individual values below the lower limit of quantification (<LLOQ) of the PCR technique will be replaced with LLOQ/2 for the calculation of summary statistics unless it is zero.

• Percentage of patients in each study group with undetectable viral load of SARS-CoV-2 on Day 8.

The percentage of patients with undetectable viral load of SARS-CoV-2, ie, patients with viral load of SARS-CoV-2 < Limit of Detection (LOD), on Day 8 will be presented by treatment group. Clopper–Pearson 95% CI will be computed for the binomial proportions.

The difference in the percentage of patients with undetectable viral load of SARS-CoV-2 on Day 8 between each dose of plitidepsin versus control arm will be presented for each dose of plitidepsin and the exact 95% CI will be computed for the difference in the percentage.

The undetectable viral load of SARS-CoV-2 on Day 8 rate between each dose of plitidepsin versus control arm will be compared using a stratified logistic regression model. The model will be adjusted for the randomisation stratification factors. The odds ratios, 95% CIs, and 2-sided p-values for the comparison of each dose of plitidepsin versus control arm will be presented.

The percentage of patients with a reduction  $\geq$  2-log in viral load or undetectable viral load of SARS-CoV-2 on Day 8 will be presented by treatment group. Clopper–Pearson 95% CI will be computed for the binomial proportions.

The difference in the percentage of patients with a reduction  $\geq$  2-log in viral load or undetectable viral load of SARS-CoV-2 on Day 8 between each dose of plitidepsin versus control arm will be presented for each dose of plitidepsin and the exact 95% CI will be computed for the difference in the percentage.

The reduction  $\geq$  2-log in viral load or undetectable viral load of SARS-CoV-2 on Day 8 rate between each dose of plitidepsin versus control arm will be compared using a stratified logistic regression model. The model will be adjusted for the randomisation stratification factors. The odds ratios, 95% CIs, and 2 sided p values for the comparison of each dose of plitidepsin versus control arm will be presented.

• Change in inflammatory biomarkers (CRP, ferritin, IL-1β, IL-6, IL-10, and TNFa) in each study group from baseline until Days 2, 3, 4, 8, and 31.

The Baseline value for the inflammatory biomarkers is defined as the value collected at the time of the clinic visit on Day 1. The percent change from Baseline at post-Baseline visits will be defined as:

• For CRP, ferritin, referred to the upper limit of normal (ULN)

% change from Baseline = 100\*((post-Baseline value/ULN) -(Baseline value/ULN))/(Baseline Value/ULN)

The values referred to ULN, ie, result/ULN, at baseline and at each post-Baseline visit, and the change from Baseline values will be summarized by Visit using standard descriptive statistics. The median values referred to ULN together with the interquartile ranges will be plotted over time by treatment group and visit. A spaghetti plot will also be used to represent the patient profile over time by treatment group.

 $\circ~$  For IL-1β, IL-6, IL-10, and TNFa

% change from Baseline = 100\*(post-Baseline value – Baseline value)/Baseline Value

The values at baseline and at each post-Baseline visit, and the change from Baseline values will be summarized by Visit using standard descriptive statistics.

The median values together with the interquartile ranges will be plotted over time by treatment group and visit.

A spaghetti plot will also be used to represent the patient profile over time by treatment group.

Data from all study visits, scheduled and unscheduled, will be listed.

• Change respect to baseline in individual serological assessments.

The percentage of patients with a serologic response anti-SARS-CoV-2 at Day 31 will be presented by treatment group. Clopper–Pearson 95% CI will be computed for the binomial proportions.

The Baseline value for the serologic response anti-SARS-CoV-2 is defined as the immunoglobulin (Ig)G Antibodies quantification value collected at the time of the clinic visit on Day 1.

Patients are considered to have a serologic response anti-SARS-CoV-2 if:

- Baseline IgG Antibodies quantification is interpreted as negative (e.g. <0.8), borderline (e.g. ≥0.8 and <1.1) or missing and increases above the established boundary (e.g. ≥1.1), following study drug administration.

- Baseline IgG Antibodies are positive and the result at Day 31 sample is at least two-folds greater than the baseline sample.

All of the other options are considered as non-serologic response.

Cutoffs for IgG Antibodies quantification will be selected at the analysis time based on the latest available specifications of the selected technology.

The difference in the percentage of patients with a serologic response anti-SARS-CoV-2 between each dose of plitidepsin versus control arm will be presented for each dose of plitidepsin and the exact 95% CI will be computed for the difference in the percentage.

The percentage of patients with a serologic response anti-SARS-CoV-2 between each dose of plitidepsin versus control arm will be compared using a stratified logistic regression model. The model will be adjusted for the randomisation stratification factors. The odds ratios, 95% CIs, and 2-sided pvalues for the comparison of each dose of plitidepsin versus control arm will be presented.

The IgG Antibodies quantification values at baseline and at Day 31 visit, and the change from Baseline in IgG Antibodies quantification values will be summarized using standard descriptive statistics.

The percent change in IgG Antibodies quantification from Baseline at Day 31 visit will be defined as:

% change from Baseline = 100\*(Day 31 value – Baseline value)/Baseline Value

Data from all study visits, scheduled and unscheduled, will be listed.

• To compare efficacy in the primary endpoint and describe safety/tolerability of pooled plitidepsin arms versus control.

Time-to sustained withdrawal of oxygen supplementation will be analysed using the Kaplan-Meier method and 25th percentile, median and 75th percentile time will be presented for the pooled plitidepsin arms and control

arm, together with 95% CIs. The 95% CIs will be computed based on Brookmeyer-Crowley method and using a log log transformation. The mean time to sustained withdrawal of oxygen supplementation and its standard error will be also presented for the pooled plitidepsin arms and control arm.

Time-to sustained withdrawal of oxygen supplementation between of the pooled plitidepsin arms versus control arm will be compared using a stratified log-rank test, including the randomisation stratification factors as covariates, ie, Geographical Region (Europe vs. Rest of the World), Charlson Comorbidity index (0-1 vs. >1) and pre-baseline Barthel index ( $\geq$ 90 versus <90) as derived using the eCRF data. The 2-sided p-values for the comparison of the pooled plitidepsin arms versus control arm will be presented.

A stratified Cox proportional-hazards regression model, including the randomisation stratification factors as covariates, ie, Geographical Region (Europe vs. Rest of the World), and Charlson Comorbidity index (0-1 vs. >1) and pre-baseline Barthel index ( $\geq$ 90 versus <90) as derived using the eCRF data, will be applied to compare results between the pooled plitidepsin arms and control arm. Hazard ratios, 95% CIs, and 2-sided p-values for the comparison of the pooled plitidepsin arms versus control arm will be presented.

The cumulative proportion of sustained withdrawal of oxygen supplementation (1-cumulative survival) will be displayed graphically for the pooled plitidepsin arms and control arm using a Kaplan-Meier curve.

• To compare efficacy in the primary endpoint and describe safety/tolerability between plitidepsin arms (1.5 versus 2.5 mg) in case both arms are significantly superior to the control.

All summary tables will be presented by treatment group. Therefore, all the data needed to compare the efficacy and safety/tolerability between plitidepsin arms (1.5 versus 2.5 mg) will be already present in the outputs created for the other efficacy and safety endpoints. Statistical comparisons between Plitidepsin arms (1.5 versus 2.5 mg) will not be performed.

• To explore the influence of risk factors or scores for clinical deterioration that were not individually included.

A subgroup analysis has been defined to assess this endpoint (see Section 7.6.4).

 Time to sustained withdrawal of supplementary oxygen (11-category WHO Clinical Progression Scale ≤4) with no subsequent reutilisation during remaining study period, before (protocol v.6) and after the amendment (protocol v.7). A subgroup analysis has been defined to assess this endpoint (see Section 7.6.4).

• Time to sustained (ie, with no subsequent readmission to Day 31) hospital discharge (since randomisation), before (protocol v.6) and after the amendment (protocol v.7)

A subgroup analysis has been defined to assess this endpoint (see Section 7.6.4).

